13.0 Vulnerable Populations

13.1 If the research involves individuals who are vulnerable to coercion or undue influence, please describe additional safeguards you will include to protect their rights and welfare. Consider the applicable items listed below:

- *If the research involves Virginia Tech students, indicate whether these are students of any of the investigators. If so, describe whether the activities will take place during class time as part of the curriculum and the steps you will take to reduce the possibility that students feel obliged to participate in order to improve their course grade. The HRPP can provide further guidance as needed. Describe whether you will request access to student records (e.g., SAT, GPA, GRE scores).*
- *If the research involves employees of Virginia Tech or the research sponsor, describe steps you will take to ensure that the employees are freely participating and describe how their data will be protected from inspection by their supervisors.*
- *If the research involves Virginia Tech NCAA athletes, you must obtain approval from the athletic department.*
- *For research involving Montgomery County Public Schools, you must obtain county approval (after obtaining contingent Virginia Tech approval). Other locales have different requirements; please check on these and describe here. Approval is typically granted by the superintendent, principal, and classroom teacher (in that order). Approval by an individual teacher is insufficient. School approval, in the form of a letter or a memorandum should be uploaded as a supporting document.*
- *If the research involves pregnant women, review “CHECKLIST: Pregnant Women (HRP-412)” to ensure that you have provided sufficient information in this protocol.*
- *If the research involves prisoners, review “CHECKLIST: Prisoners (HRP-415)” to ensure that you have provided sufficient information in this protocol.*

- *If the research involves persons who have not attained the legal age for consent to treatments or procedures involved in the research (minors), review the “CHECKLIST: Minors (HRP-416)” to ensure that you have provided sufficient information in this protocol.*
- *If the research involves cognitively impaired adults, review “CHECKLIST: Cognitively Impaired Adults (HRP-417)” to ensure that you have provided sufficient information in this protocol.*

This research study will not include any vulnerable populations.

14.0 Number of Subjects

14.1 Indicate the total number of subjects to be enrolled and how this number was determined (e.g., sample size calculation [show], number of available subjects in a finite pool, number of tests funding award would allow):

G*power (Faul et al., 2007) determined the necessary sample size for this experiment - given a medium expected correlation of 0.4, we would need 42 participants (alpha = 0.01, Power = 0.8). We therefore propose to collect data from 50 participants.

14.2 If this is a multi-site study, indicate the number of subjects to be enrolled at this site and the total to be enrolled from all sites:

N/A

14.3 If applicable, indicate the number of potential subjects you expect to screen for enrollment, and the number of subjects you will need to complete the research procedures:

N/A

14.4 If the study has more than one procedure, indicate the total number of subjects to undergo each procedure separately:

N/A

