2.0 Objectives

2.1 Describe the purpose, specific aims, or objectives of this study:

This study directly tests the ability to modulate neural activity as a function of AUD severity using real-time fMRI.

2.2 State the hypotheses to be tested:

We hypothesize that individuals with lower AUD severity will have a significantly higher correlation (indicating better modulation ability) than individuals with higher AUD severity.

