5.0 Study Design and Statistical Analysis Plan

5.1 *Describe the basic study design/approach (e.g., qualitative study using five focus groups of first year students to describe assimilation into the university community; randomized controlled trial of a behavioral change intervention to increase dietary intake of whole grains; pre- post-test evaluation of new pedagogical techniques to improve adult literacy):*

50 participants who drink alcohol, including those with AUD, will be recruited and consented into a real-time study intended to assess the relationship between AUDIT score and neural modulation. There are two neuromodulation tasks, which they may complete one or both of. The "DMN" neuromodulation task has them attempt to "focus/wander". The "BAAD" neuromodulation task instructs participants to modulate their brain activity toward a craving for alcohol or orient it toward a future goal. If there is time, and the participant is interested, they will also be given the opportunity to complete the other task to which they weren't initially assigned.

5.2 *Describe corresponding data analysis plan/approach (e.g., content analysis of focus group transcripts; descriptive analysis followed by linear regression modeling; nonparametric analysis of pre- and post-test measures):*

GLM-based analysis will be performed using AFNI (Cox, 1996). We will perform slice timing correction, motion correction, and spatial smoothing (Gaussian kernel with full-width-at-half-maximum of $2.0 \times$ the voxel size). The stimulus paradigms will be convolved with an ideal hemodynamic response function, and linear regression analysis will be performed to obtain linear regression coefficients (beta-weights) and t-statistic maps. In addition, we will perform support vector machine analysis using the 3dsvm AFNI plugin software we have developed.

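### The sample size of 42 does not follow from its printed inputs: r = 0.4 at alpha 0.01 and 80% power needs 59 (one-sided) or 68 (two-sided), so 50 participants fall short of the stated power

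*Combined protocol and SAP*

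**What the plan says.** Section 14.1 (Number of Subjects) reports a G*Power calculation: "given a medium expected correlation of 0.4, we would need 42 participants (alpha = 0.01, Power = 0.8". The next sentence draws the enrolment target from it: "We therefore propose to collect data from 50 participants". Neither the number of tails nor the test model is given.

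The quantity being powered can be inferred from other sections. Section 5.1 describes the study as "intended to assess the relationship between AUDIT score and neural modulation". The hypothesis in 2.2 is directional: "individuals with lower AUD severity will have a significantly higher correlation (indicating better modulation ability) than individuals with higher AUD severity". Section 3.3 says each person's modulation ability will be compared with the AUDIT score. Section 5.2, the data analysis plan, covers image preprocessing, regression maps and support vector machine analysis; it gives no test, alpha or number of tails for the AUDIT association. Section 4.1 lists the endpoints as N/A.

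Section 14.3 asks for "the number of subjects you will need to complete the research procedures", and 14.4 asks for the number undergoing each procedure. Both are answered N/A.

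**The concern.** All the numerical inputs are printed in one sentence, so the result can be checked directly. A requirement of 42 looks too small for a correlation of 0.4 at an alpha as strict as 0.01.

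This sentence is the only justification of the study size. It is also the only place where the plan fixes an error rate and an effect size for its single objective. If the figure is wrong, a reader who takes 14.1 at face value would treat a null result as having had at least 80% power against r = 0.4. The conclusion that modulation ability does not depend on AUD severity would then carry more weight than the design supports.

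**Working it through.** **Inputs (section 14.1).** Correlation r = 0.4, alpha = 0.01, power = 0.80, stated n = 42, planned n = 50. The number of tails is not stated, so both cases are run. No dropout allowance is applied, because none is given. The hypothesised association is negative; r below is its absolute size.

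**Attempt to reproduce 42, Fisher z.** The formula is n = ((z_alpha + z_power) / atanh(r))² + 3, with atanh(0.4) = 0.4236 and z_power = 0.8416.

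- Two-sided, z_alpha = 2.5758: (3.4174 / 0.4236)² + 3 = 68.1, so 69.
- One-sided, z_alpha = 2.3263: (3.1680 / 0.4236)² + 3 = 58.9, so 59.

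**Other standard models.** The exact calculation integrates the density of the sample correlation under bivariate normality beyond the t-based critical value. The noncentral-t model treats the predictor as fixed.

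| Model, r = 0.4, alpha 0.01, 80% power | One-sided n | Two-sided n |
|---|---|---|
| Exact bivariate normal | 59 | 68 |
| Fisher z | 59 | 69 |
| Noncentral t | 56 | 65 |
| One-predictor regression F test | – | 65 |

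Exact power either side of the threshold is 0.799 at 58 and 0.807 at 59 (one-sided), and 0.796 at 67 and 0.804 at 68 (two-sided). No version gives 42. The smallest, 56, is 14 above the stated 42 and 6 above the planned 50.

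**Exact power at the stated and planned sizes (r = 0.4, alpha 0.01).**

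| n | One-sided | Two-sided |
|---|---|---|
| 42 | 63.4% | 53.3% |
| 50 | 72.6% | 63.4% |

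Fisher z check at n = 50, two-sided: 0.4236 × √47 − 2.5758 = 2.904 − 2.576 = 0.33, which gives 62.9%. The noncentral-t model at n = 50 gives 74.9% one-sided and 65.7% two-sided, still below 80%.

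**Smallest correlation with 80% power at alpha 0.01 (exact).** At n = 50 it is 0.43 one-sided or 0.46 two-sided. At n = 42 it is 0.46 or 0.50.

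**What would give 42?**

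- Changing only the correlation to 0.5, two-sided: Fisher z gives (3.4174 / 0.5493)² + 3 = 41.7, so 42. Exact power is 0.798 at 41 and 0.811 at 42.
- Changing only alpha to 0.05 does not give 42: the exact n is 37 one-sided or 46 two-sided. For 80% power at n = 42 and r = 0.4, alpha would have to be about 0.033 one-sided or 0.066 two-sided.
- Changing two inputs can also give it: r = 0.4 at one-sided alpha 0.05 and 85% power needs exactly 42.

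**The case against.** The strongest reply is that the shortfall at 50 depends on r = 0.4 and alpha = 0.01 both being the intended inputs, and one of them may be a misprint. If r = 0.5 was used, 50 participants give about 89% power (two-sided, alpha 0.01). If two-sided alpha 0.05 was meant, they give 83.5% power for r = 0.4. This stands as a limit on what can be said about the cause. The match with r = 0.5 is a possible explanation and no more, since other combinations also give 42. It does not rescue the text: as printed, the four numbers contradict one another, and a reader cannot tell whether 50 is enough.

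A second point is that 63% or 73% is itself an upper figure, because it assumes all 50 people enter one correlation. Participants may complete one or both of two tasks, and no number per task is given. If only 35 were analysed (an assumption), exact power would be 54% one-sided or 43% two-sided; with 25, it would be 37% or 28%. This is correct and should qualify any restated power, but it widens the gap.

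A third point is that letting the authors change the effect size or alpha invites fitting the inputs to a fixed 50. That is fair. The text calls 0.4 the expected value, and the documents offer no basis for 0.5. Another input should be printed only if the original calculation output shows that it was used, or if the choice is justified on its own terms.

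Finally, how a null result would be read is a forecast, since the plan has no rule for interpreting one. The arithmetic does not depend on it.

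**Conclusion.** The concern holds. The 42 in section 14.1 is wrong for its printed inputs under every standard one-correlation model tried. The exact requirement is 59 one-sided or 68 two-sided, that is 17 or 26 more than stated and 9 or 18 more than the planned 50. At 50, the chance of missing a true correlation of 0.4 is about 27% one-sided or 37% two-sided, against the 20% implied.

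This rests on the printed r = 0.4 and alpha = 0.01, a single test of one correlation against zero, and usable data from all 50. Fewer analysed participants would lower power further. Which input was misprinted cannot be settled from the documents. Nothing elsewhere in them repairs the figure, and because it is the sole support for the study size it must be corrected.

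**What to change.** Correct section 14.1 without changing enrolment. Retrieve the original calculation output first, then use whichever of these applies:

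1. **Default, keeping r = 0.4 and alpha 0.01.** Replace 42 with 59 (one-sided) or 68 (two-sided). State that 50 analysed participants give about 73% or 63% power for r = 0.4, or 80% power for a correlation of about 0.43 or 0.46.
2. **If the output shows that 0.5 was the input.** Print 0.5 with n = 42, two-sided alpha 0.01, and give the reason for expecting 0.5.
3. **If the test will be at two-sided alpha 0.05.** Print that alpha with a reason, a required n of 46 for r = 0.4, and power of about 84% at 50.

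In each case name the test and the number of tails, and make the power statement conditional on the number with usable data in the analysis that it describes. Section 5.2 currently contains no test of the AUDIT association, so add one there with the same alpha and tails as 14.1.

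The cost is wording only and no extra participants. Under the default the stated power becomes less favourable.

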15.0 Recruitment Methods

15.1 Describe when, where, and how you will recruit potential subjects:

Participants will be recruited from the community via posted flyers, word of mouth, and electronic advertisements (e.g., Craigslist, Facebook). Participants may also be recruited from a pre-existing database of individuals who have given consent to be contacted about studies.

15.2 Describe the source of subjects (for example, clinic patients with specific conditions, students in the library, community members at a gathering, or members of a local gym):

Participants will be recruited from the community via posted flyers, word of mouth, and electronic advertisements (e.g., Craigslist, Facebook). Participants may also be recruited from a pre-existing database of individuals who have given consent to be contacted about studies.

15.3 Describe the methods that you will use to identify potential subjects:

Participants will be recruited from the community via posted flyers, word of mouth, and electronic advertisements (e.g., Craigslist, Facebook). Participants may also be recruited from a pre-existing database of individuals who have given consent to be contacted about studies.

15.4 Describe materials that you will be use to recruit subjects. Attach copies of these documents with this protocol in Protocol Management and be sure to include the IRB protocol number on each document.

- *For flyers, attach the final copy of printed flyers.*
- *For Virginia Tech News, Facebook postings and ads, newspaper ads, websites, MTurk/SONA/online survey systems, etc., attach the final wording and graphics to be used.*
- *For email recruitments, please include the subject line.*
- *For advertisements meant for audio broadcast, please submit the wording of the advertisement prior to taping (to avoid having to re-record with approved language) and submit the final recorded version for IRB review before use.*
- *Describe any compensation to subjects. Separate compensation into appropriate categories, such as: reimbursement for expenses, time and*

effort, and additional incentives for study participation. For each category, specify the amount (including any pro-rated amount), schedule, and method of payment.

Recruitment flyer included in protocol submission.

Participants are compensated \$30.00 per hour of distributed via Clincard or approved petty cash accounts. Payments will be submitted the same day as the subject's MRI session. If a participant is withdrawn or voluntarily discontinue, their compensation for the study will be pro-rated accordingly.

16.0 Withdrawal of Subjects

16.1 Describe circumstances under which you anticipate subjects could be withdrawn from the research without their consent:

Participants may be withdrawn from the research without their consent if they become ineligible based on inclusion/exclusion criteria or learning of a contraindication for continuing

If the participant is not complying with FBRI building policies and/or insists on leaving with a BAC >0.08 g/dL, local security will be contacted however, the participant will not be named to avoid breaking confidentiality. They will also complete an Alcohol Withdrawal Symptom questionnaire. A score of >23 on this checklist requires medical oversight for alcohol withdrawal and will trigger the research staff to contact study physician [name] for guidance.

16.2 If applicable, describe any procedures for orderly termination (e.g., discontinuation of a study drug or debriefing after a behavioral intervention):

If a participant is withdrawn from the study, he or she will be informed that we have collected all the data required from their participation. If a participant is withdrawn or voluntarily discontinue, their compensation for the study will be pro-rated accordingly.

16.3 Describe procedures that you will follow when subjects withdraw from the research, including partial withdrawal from procedures with continued data collection (e.g., participant declines to continue with regular blood draws, but continues with periodic behavioral questionnaires):

If a participant is withdrawn or discontinued, they will be withdrawn from the entire study.

17.0 Risks to Subjects

17.1 List the reasonably foreseeable risks, discomforts, hazards, or inconveniences to the subjects related to the subjects' participation in the research. Include for the IRB's consideration a description of the probability, magnitude, duration, and reversibility of the risks. Consider physical, psychological, social, legal, privacy, and economic risks. Do not indicate "No risk" or "N/A." Instead, for studies with very low risk (e.g., anonymous online questionnaire on a mundane topic) indicate "The investigators are not aware of any risks from participation in this study." or "No more than risks than are found in everyday life." The example consent form presents a tabular method for risk information, which you can also use here. Common risk types include:

- *Physical (e.g., potential for pain, discomfort, infection)*
- *Psychological (e.g., potential for stress, discomfort, and/or embarrassment)*
- *Social (e.g., potential for discrimination or stigmatization and disruption of personal and family relationships)*
- *Legal (e.g., potential for disclosure of illegal activity, negligence)*
- *Privacy (e.g., potential for personal information being accessed, used, or disclosed without the subjects' knowledge or consent, breach of confidentiality/security)*
- *Economic (e.g., potential for individuals to lose access to economic services, employment, insurability)*

The risks associated with fMRI are the same as those with conventional MRI. Movement or heating of metallic implants is a potential risk, and so subjects will be screened to exclude people with metallic implants, fragments, or pacemakers. Some individuals experience claustrophobic reactions in the scanner. Any subject experiencing claustrophobia will be removed from the scanner immediately.

The fMRI scanner produces loud noises which could be harmful to the subject. Participants will be required to wear headphones to minimize the noise generated by the scanner.

There is no invasive component to this study, such as IV catheters, and so discomfort, bruising, or infection are not risks. The Siemens 3 T scanner has been approved by the FDA. However, there may be additional risks associated with scanning at 3 T compared to the conventional clinical scanners in the 1.5-2.0 T range. These include:

1. Effect of the static field. There is no conclusive evidence for irreversible or hazardous bioeffects to acute, short-term exposures of humans up to 2.0 T (Shellock and Kanal, 1996). Studies have indicated some side-effects at 4.0 T, namely unusual sensations including nausea, vertigo, and metallic taste (Schenck, 1991). However, there is no evidence that this is either irreversible or harmful. If subjects experience unusual sensations, they will be withdrawn.
2. Effect of the gradient field. MRI operates by rapidly changing small additional fields, called gradients. This will induce small electrical currents in any conductor, and thus could theoretically induce mild peripheral nerve stimulation. However, this is not substantially different at higher magnetic fields since the gradients are separate from the main magnet. There is no evidence that the effect of the gradients is any different at 3 T than at 1.5 T. However, if subjects experience peripheral nerve stimulation, e.g. tingling or twitching, they will be withdrawn.
3. Effect of the RF electromagnetic field. The higher magnetic field strength requires that higher RF frequency pulses are used to excite the protons in the subject's brain. The limits of RF energy that can be safely given to humans has been clearly defined by the FDA: a. The exposure to RF energy below the level of concern is an SAR of 0.4 W/kg or less averaged over the body, and 8.0 W/kg or less spatial peak in any 1 g of tissue, and 3.2 W/kg or less average over the head; or b. The exposure to RF energy that is sufficient to produce a core temperature increase of 1 degree C and localized heating to no greater extent than 38 degrees C in the head, 39 degrees C in the trunk, and 40 degrees C in the extremities, except for patients with impaired systemic blood flow and/or perspiration. We will adhere to the recommendations for the head, which is also monitored by a Siemens built-in monitor.

While in the scanner, subjects will alternate between a resting state and a stimulus-induced state. It is unlikely participant will experience discomfort during these tasks, however, subject comfort will be assessed routinely and subjects will be allowed to discontinue any session at any time.

The subject may communicate with the experimenter at any time: 1) before, in between, or after a scan via an intercom device between the scanner and control room, and 2) during a scan via a pneumatic squeeze bulb located in the scanner that triggers an alarm in the control room. Subjects who report discomfort and wish to discontinue their participation will be immediately withdrawn from the scanner. Subjects who are withdrawn from the study will be compensated for their participation to that point.

Because participants may not participant with a BAC over 0.003, they may experience alcohol withdrawal symptoms.

17.2 Indicate the measures you will use to minimize risks and monitor subjects for safety. (e.g., asking a subject at regular intervals to rate how they are feeling from 1 to 10, or to slowly crouch in order to check their balance.)

General Safety: Despite our best efforts, we recognize that in rare circumstances participants may experience extreme distress with sudden onset. The PI and study staff are trained to recognize and deescalate such situations. All personnel are instructed to exercise judgment and follow our safety protocol where indicated.

Advanced MR/Operator Training: Required for those persons wishing to conduct research on the HNL MRIs. Training will consist of presentations, observation, and hands-on practice. Topics will include safety and emergency procedures, subject screening and preparation, scanner set-up and operation, and troubleshooting. Each person must also complete at least 4 hours of observation (to include 2 different studies) and at least 16 hours of supervised scanning (to include 4 different studies). Certification will be granted upon completion of the training and passing of a competency exam

In some cases for demonstration, the volunteers will be provided with their own structural brain images to take home on CD, as is done with many of our approved IRB protocols. These images are not diagnostic quality and are provided to subjects routinely after most approved protocols. They are informational only and are not intended to be used as diagnostic tools.

Alcohol Withdrawal: In addition, participants who are not drinking alcohol may experience alcohol withdrawal symptoms. They will complete the Alcohol Withdrawal Symptom Checklist (AWSC), a validated 17-item checklist of symptoms in which the participant rates their experience from 0 ("Not at all") to 4 ("Extreme"). A score of >23 on this checklist requires medical oversight for alcohol withdrawal and will trigger the research staff to contact [name]. [name] will speak with the participant to determine appropriateness and safety to continue in the study and to provide medical consultation and/or a referral to a clinic/primary care physician. If the participant produces a score of >23 on the checklist, [name] will be contacted to assess the participant's risk and refer as necessary. We have successfully implemented these procedures with [name] in our previous and ongoing studies.

17.3 If applicable, indicate which procedures might have risks to the subjects that are currently unforeseeable. This will be rare, and usually applicable when testing a new drug or device or a new use of an existing drug or device:

N/A

17.4 If applicable, indicate which procedures might have risks to an embryo or fetus should the subject be or become pregnant:

While no data have conclusively determined MR imaging to be unsafe for developing fetuses, it has also not been determined to be safe. Thus, consistent with the guidance document of the American College of Radiology (Kanal et al., 2013), we believe the benefit to the participant does not outweigh potential unknown risks to the developing fetus. Thus, we exclude pregnant women to ensure the safety of participants.

17.5 If applicable, describe risks to others who are not subjects (e.g., collection of sensitive health data that might affect sexual partners if disclosed, mandatory reporting of abuse, DNA testing that might affect family members or relationships):

N/A

